### *Craving assessment*

Craving was scored through a brief scale composed of five items (1, 2, 4, 5, and 13) of the Obsessive-Compulsive Cocaine Use Scale, also known as the Obsessive-Compulsive Cocaine Scale (OCCS), which are based on the Obsessive-Compulsive Drinking Scale (Anton et al., 1995;Anton et al., 1996;Anton, 2000), as proposed by Hormes et al. (Hormes et al., 2012) and

Vorspan et al. (Vorspan et al., 2012). These five-item scales assess craving in a narrow sense according to De Wildt et al. (de Wildt et al., 2005).

Through this brief scale it is possible to quantify thoughts and feelings (obsessions), and behavioral intentions (de Wildt et al., 2005), answered on a scale ranging from 0 to 4, resulting in a total score between 0 and 20. Patients are questioned on how much of the time (total per day), when the drug is not used, is occupied by thoughts, ideas, desires, or impulses related to crack-cocaine and its effects; how frequently these thoughts, ideas, desires, or impulses related to crack-cocaine and its effects occur; how much distress or disturbance these ideas, thoughts, impulses or desire related to crack-cocaine use cause when the person is under withdrawal; how much effort they have to make to resist these thoughts, ideas, desires, or impulses, or how much energy they have to spend to think of something else when they enter the mind under withdrawal; and finally ask about their drive to use crack-cocaine.

The OCCS was applied in the week before the beginning of the real or sham-tDCS treatment, during the treatment (second, third and fourth weeks) and in the week after the end of the brain stimulation application, resulting in five time-points measurements.

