### *Statistical Analysis*

We powered the study for a medium effect size based on the results of our previous study (Batista et al., 2015) in which the effect size (partial  $\eta^2$ ) for the main within-subject factor in the respective two-way ANOVA with repeated measures was 0.10384 when comparing craving scores once before, twice during and once after 5-sessions of tDCS (four time-points). The tDCS electrode montage was identical in the studies, and patient populations of crack-cocaine users were similar. We used the correction for SPSS input into the G\*Power 3.1.9.2. With this effect size, for the two-way mixed model ANOVA of the present study with the within factor craving measurements, the

between-subject factor tDCS condition, the dependent variable craving score, and craving measurements x condition interaction as the primary outcome parameter, with a power of 80%, and a two-sided probability of a type I error of 5%, the resulting minimum sample size was 30 participants. To account for waiving or dropouts, which were expected to be very common in this condition, we increased the estimated sample size to approximately 10%, resulting in 33 subjects in total (approximately 16 to 17 subjects in each group).

Most of data (age, patterns of crack-cocaine use, 5-items OCCS) were normally distributed according to the D'Agostino & Pearson normality test, thus they were analyzed by parametric tests. Between-group (sham- and real tDCS) comparisons were conducted by unpaired *Student's t*-tests. For all other non-parametric data (gender, schooling, employment, marital state and tobacco use), Chi-square or Fisher tests were used to compare sham and real tDCS groups.

Besides the two-way ANOVA with repeated measures followed by Bonferroni-corrected t-tests, linear regression analyses were done over craving scores obtained along the 4-week treatment (five time-points measurements) for both groups. Additional comparisons between initial and final OCDS scores were done by paired t-tests for each group, and differences between final and initial scores were compared between sham-tDCS and real tDCS groups with unpaired t-test. Effect sizes were calculated using Cohen's *d* and corrected by Hedges's  $g_s$  for unpaired and Hedges'  $g_{av}$  for paired t-tests (Lakens, 2013).

A two-tailed p-value of 0.05 or less was considered to indicate statistical significance. SPSS Statistics Base 24.0 (SPSS Inc, USA) and GraphPad Prism

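### The t-tests that follow the craving ANOVA use single-step Bonferroni; Holm's step-down version gives the same 5% family-wise protection and never rejects less, so it is a cheap improvement once the family of comparisons is stated.

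*Combined protocol and SAP*

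**What the plan says.** Craving is scored once a week, "resulting in five time-points measurements" (Craving assessment): one before stimulation, three during and one after (Procedures). The primary parameter is the single measurement-by-condition interaction in a two-way mixed ANOVA, and the sample size rests on that test alone, "resulting in 33 subjects in total (approximately 16 to 17 subjects in each group").

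The follow-up tests appear in half a sentence of Statistical Analysis: "Besides the two-way ANOVA with repeated measures followed by Bonferroni-corrected t-tests". The section does not say whether these compare the arms at each visit or the visits within an arm, how many there are, or whether a step-down form is used. It claims no power for them.

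The same paragraph lists other craving analyses with no correction stated: linear regressions, paired initial-to-final t-tests in each arm, and an unpaired t-test of the arms on the change from first to last score. The general rule is "A two-tailed p-value of 0.05 or less was considered to indicate statistical significance".

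**The concern.** The interaction test says only that the two craving profiles differ. The corrected t-tests are the plan's means of locating the difference, either at particular visits between arms or between particular visits within an arm. With about 16 or 17 patients per arm these tests are weak, so the choice of correction is worth a look.

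Single-step Bonferroni holds every test to 0.05 divided by the number of tests, whatever the other tests show. Holm applies that threshold only to the smallest p-value and relaxes it at each further rejection. It needs no extra assumption and uses the same t-tests. What is at stake is some ability to make statements about several visits, given up with no gain in error control. The validity of the trial is not at stake.

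**Working it through.** **1. The plan's own figure.** Inputs from Statistical Analysis: the partial eta-squared "for the main within-subject factor in the respective two-way ANOVA with repeated measures was 0.10384"; the SPSS convention for the effect size ("We used the correction for SPSS input into the" sample-size program); 80% power; two-sided 5%. Two groups (k = 2) and five visits (m = 5). Sphericity is assumed.

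- f² = 0.10384 / (1 − 0.10384) = 0.1159, so f = 0.340.
- λ = f²(N − k)(m − 1) = 0.1159 × 28 × 4 = 12.98 at N = 30, with 4 and 112 degrees of freedom.
- Power is 81.8% at N = 30, 78.4% at N = 28 and 86.2% at N = 33.

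With equal arms, the stated minimum of 30 is reproduced, and 30 × 1.1 = 33. This calculation concerns only the interaction. The follow-up correction does not enter it.

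**2. Why Holm dominates.** Order the m p-values. Compare the smallest with 0.05/m, the next with 0.05/(m − 1), and so on, stopping at the first failure.

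- Every threshold is at least 0.05/m, so whatever Bonferroni rejects, Holm rejects.
- Suppose m₀ nulls are true. When the first true null is wrongly rejected, at most m − m₀ false ones have gone before it. Its threshold is therefore at most 0.05/m₀, and the sum over the m₀ true nulls is at most 5%. Nothing is assumed about dependence.

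Both statements hold for any family of two or more tests, so they do not depend on what the plan intended.

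**3. Size of the gain for one possible family.** Assumptions, none given in the documents: one unpaired between-arm t-test per visit, five visits, 16 vs 17 patients, normal scores with equal SDs, equal correlation of 0.5 or 0.7 between visits, no baseline difference.

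Bonferroni can be computed directly. Each test is at 0.05/5 = 0.01 on 31 degrees of freedom, critical |t| = 2.744. At 1.0 SD the noncentrality is √(16 × 17/33) = 2.871 and power is 55.6%. At 0.7 SD the noncentrality is 2.010 and power is 25.1%.

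Holm needs simulation (20,000 to 60,000 trials per scenario). Power at the final visit:

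| True difference at the four later visits (SD) | Bonferroni, 5 tests | Holm, 5 tests |
|---|---|---|
| 1.0 at all four | 55-56% | 62-63% |
| 0.7 at all four | 25% | 28-29% |
| 0.5, 0.8, 1.0, 1.0 | 55-56% | 59% |
| 0.25, 0.5, 0.75, 1.0 | 55-56% | 56-57% |

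- Mean number of the four later visits detected, Bonferroni vs Holm: about 2.2 vs 2.5 in the first row and 1.0 vs about 1.15 in the second.
- Chance of at least one rejection: the same for both, because the first Holm step is also 0.01. In the first row it is about 85% at correlation 0.5 and 79% at 0.7.
- Family-wise error when no visit differs: about 3.5% to 4.5% for both.

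**4. The other possible family.** Five visits give 5 × 4/2 = 10 pairwise comparisons within an arm. With 17 patients and assumed falls of 0.4 to 1.0 SD, the mean number of rejections was 2.48 (Bonferroni) vs 2.71 (Holm) at correlation 0.5, and 3.75 vs 4.14 at 0.7.

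**5. Keeping two changes apart.** Dropping the baseline visit leaves four tests. At 1.0 SD throughout, Bonferroni over four (0.05/4 = 0.0125) already gives 59%, and Holm over four gives 68-69%. The step from 56% to 59% comes from the smaller family, not from Holm.

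**6. The planned change-score test.** On the same assumptions, the SD of the change is √(2(1 − ρ)) times the visit SD: 1.0 at ρ = 0.5 and 0.775 at ρ = 0.7. At 0.05, the test of final-minus-initial change has 79% and 95% power for a final difference of 1.0 SD, and 49% and 71% for 0.7 SD.

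**The case against.** The strongest reply is that this is a textbook fact with little practical weight here. Most of its parts stand.

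- **The family is inferred.** A reader might take it that the follow-up tests compare the arms visit by visit, each at 0.01. The section does not say so. It does describe between-group comparisons by unpaired t-tests, so the reading is reasonable, but the power figures in step 3 depend on it. The dominance of Holm does not.
- **End of treatment is covered elsewhere.** A reader might infer that Bonferroni weakens the trial's ability to show a difference after the last session. The plan has a separate, uncorrected t-test on the change score, with more power under the same assumptions than either corrected final-visit test.
- **The larger gains need a favourable pattern.** They arise when several visits differ strongly. The plan's hypothesis that more sessions give a larger effect fits gradual growth at least as well, and there the gain at the final visit is about 1 point.
- **Sample size is the main limit.** A reader might blame the correction for the low power per visit. At 0.7 SD throughout, power is 25% with Bonferroni and still only 28-29% with Holm.
- **Timing.** The document is dated October 2018, recruitment ended in April 2018, and the section is written in the past tense. A switch to a less strict correction now is likely to be post hoc.

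What survives is that, for whatever family was meant, Bonferroni gives up some rejections and gains no error control in return.

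**Conclusion.** The point holds as a free or cheap improvement. Bonferroni is valid and conservative, and the documents do not support calling its use an error or saying that it undermines the trial's conclusions. The primary interaction test, the sample size and the change-score t-test are all unaffected.

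That Holm is at least as good is certain. The size of the gain is conditional on the assumed between-arm family, effects and correlations: about 7 points of final-visit power at 1.0 SD throughout, 3 to 4 points at 0.7 SD throughout, about 1 point with gradual growth to 1.0 SD, and none for the chance of finding any difference. The benefit is confined to statements about several visits. The unstated family matters at least as much as the choice of correction, because neither method can be applied in a checkable way until it is named.

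**What to change.** In Statistical Analysis, replace the Bonferroni-corrected t-tests with *Holm-corrected t-tests (step-down, family-wise 5%)*. State the family of post-ANOVA comparisons the investigators intend (arms at each visit, or visits within an arm, and how many), and report Holm-adjusted p-values within it. The interaction stays the primary parameter.

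If the change is made after data have been seen, disclose it as such and show the Bonferroni results alongside.

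Limiting the family to the four visits after stimulation begins is a separate decision. If it is taken, justify it separately and do not credit its gain to Holm.

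Cost: a line or two of wording, with adjusted p-values from the same t-tests. Holm has no equally simple simultaneous confidence intervals, but the plan reports none.

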### *Participants*

All subjects were informed about the purposes of the experiment by the principal investigator and signed a written consent before entering the study.

Thirty-five patients, 29 men and 6 women, who met DSM V criteria for cocaine (crack) use disorder were recruited between June of 2015 and April of 2018 from three specialized clinics for drug use disorder treatment (one public and two private hospitals) from Espírito Santo State, Brazil. They all received standard treatment given by the clinics, consisting of psychosocial approaches – conducted by a professional team of psychologists, nurses, social workers and physicians – sometimes combined with adjunctive pharmacotherapy including benzodiazepines, B-complex vitamins, disulfiram and, if necessary, antidepressants, anxiolytics, antipsychotics, antihypertensive and gastric medication. It must be mentioned that in the public hospital, from where half of the patients was recruited, they were not allowed to have any medication, except non-opioid pain relievers when absolutely necessary, after they had been admitted to the hospital. Therefore, half of the patients were free of medication during the sham- or DC-stimulation. From the other half patients coming from the two private clinics, few of them were medicated (antipsychotics, antidepressants or mood stabilizers) during brain stimulation procedures.

There were two dropouts in the sham-tDCS group that were excluded after randomization. One patient escaped from the treatment facility and the other had to be discontinued because of precocious discharge from the clinic for misconduct.

The inclusion criteria for this study were: (1) male and female patients over the age of 18 years; (2) met criteria for crack-cocaine use disorder according to the ICD-10 Classification of Mental and Behavioral Disorders and the Diagnostic and Statistical Manual of Mental Disorders, fifth edition, as

determined by clinical evaluation; (3) in stable clinical condition with no need for emergency care; (4) able to read, write, and speak Portuguese; and (5) no severe withdrawal signs or symptoms at baseline.

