### *Procedures*

Those patients who were eligible according to inclusion and exclusion criteria described above and agreed to participate in this study signed an informed consent sheet. All data were originally acquired from participants entering this single research center clinical trial to investigate the efficacy of tDCS treatment.

After global physical and clinical examination subjects were randomly assigned to one of the two groups (sham- and real tDCS) in a 1:1 ratio using a computer-generated block randomization sequence that was kept with the unblinded study coordinator (not involved in the recruitment). The co-investigator conducting treatments was only given a list of 5-number blinding codes to be loaded to the DC-stimulator before each session of brain stimulation. The device is previously settled with specific settings for the study.

After patients had been admitted to the hospitals, they were maintained under regular treatment for 30 days in average or until they had reached a global clinical stabilization, to have them started in the sham- or real tDCS treatments. The brain stimulation application was then performed in one 20-min session a day, every other day, including weekends, up to a total of 10

sessions, always in the afternoon period, in the following five weeks and they were followed-up after the end of the stimulation treatment for up to 60 days after their discharge from the hospitals.

Craving was measured once a week over five weeks (once before the beginning of the stimulation sessions, three times over the stimulation sessions and once more after the end of stimulation sessions) with a total of five time-points measurements. Relapses were collected after discharge from the hospital up to 60 days after intervention.

Participants and experimenters were blinded for brain stimulation assignments from the beginning of the study protocol up to the end of the 60-days follow-up after the end of sham- or real tDCS treatment, resulting in a double-blind experimental design.

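### The supplementary linear regressions over five weekly craving scores name no model for within-patient correlation, so any slope p-value or CI read from them as ordinary regression would be miscalibrated in an unknown direction (minor)

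*Combined protocol and SAP*

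**What the plan says.** Under Procedures, "Craving was measured once a week over five weeks (once before the beginning of the stimulation sessions", with three more scores during stimulation and one after it. All five come from the same patients.

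Under Statistical Analysis, the primary test is a two-way mixed ANOVA with the "craving measurements x condition interaction as the primary outcome parameter". The regressions are an addition to it: "Besides the two-way ANOVA with repeated measures followed by Bonferroni-corrected t-tests", the plan reports that "linear regression analyses were done over craving scores obtained along the 4-week treatment (five time-points measurements) for both groups". The same paragraph then lists two change analyses. In the first, "Additional comparisons between initial and final OCDS scores were done by paired t-tests for each group". In the second, "differences between final and initial scores were compared between sham-tDCS and real tDCS groups with unpaired t-test".

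The section closes with one significance rule, a two-tailed p of 0.05 or less, and makes no exception for the regressions. No random effect, GEE, robust standard error or per-patient slope is mentioned for them.

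**The concern.** The paragraph specifies repeated measures for the ANOVA and pairing for the within-group t-tests. Only the regression is left without a method for correlated scores, so its plain reading is ordinary least squares. That can be done in two ways.

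- **Individual scores.** With 16 to 17 patients per arm there are 16 × 5 = 80 to 17 × 5 = 85 scores, all treated as independent.
- **Weekly group means.** The line passes through five points with 5 − 2 = 3 residual degrees of freedom and ignores correlation between weeks.

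The slope estimate itself is reasonable with complete data. Its standard error is right only for particular correlation patterns. If it is too large, a real trend is hidden. If it is too small, a trend is overstated. A reader cannot tell which, because the documents give neither an SD nor a correlation. The regression is also the only listed analysis that summarises all five scores as a slope.

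**Working it through.** **The plan's own figure.** The documents give no figure for the regressions. The only related figure is the sample size for the primary interaction. With partial η² = 0.10384, f² = 0.10384/(1 − 0.10384) = 0.1159. With two groups, five time points and the SPSS-type noncentrality f²(N − 2)(5 − 1), N = 30 gives λ = 0.1159 × 28 × 4 = 12.98 on 4 and 112 df, and power 81.8%. The stated 30 is reproduced, and 30 × 1.10 = 33. The regressions do not enter this calculation.

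**Inputs and assumptions.**
- Five equally spaced weekly scores per patient (Procedures).
- 35 recruited less 2 excluded = 33 patients (Participants). The split is not given; 17 real and 16 sham is assumed.
- Correlation is not given. Three families are assumed: constant correlation (CS), AR(1), and random patient intercepts and slopes.

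**Standard error, individual scores.** Let c = (−2, −1, 0, 1, 2), so c′c = 10. Let V be the covariance of one patient's five scores and n the patients in an arm.
- True slope variance: c′Vc/(100n).
- Average variance that ordinary regression reports: E[RSS]/((5n − 2) × 10n), where E[RSS] = n·tr(V) − 1′V1/5 − c′Vc/10.

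Three examples show the change of direction:
- *CS 0.5, n = 17.* c′Vc = 5, 1′V1 = 15, E[RSS] = 85 − 3 − 0.5 = 81.5. Reported variance is (81.5/83)/170 = 0.982/170; true variance is 5/1700 = 0.5/170. SE ratio √(0.982/0.5) = 1.40: too wide.
- *AR(1) 0.5, n = 17.* c′Vc = 12, 1′V1 = 11.125, E[RSS] = 85 − 2.225 − 1.2 = 81.575. SE ratio √(0.983/1.2) = 0.905: too narrow.
- *Random slopes, n = 16* (intercept variance 4 at mid-course, slope SD 1.5, residual variance 4). c′Vc = 225 + 40 = 265, tr(V) = 62.5, 1′V1 = 120, E[RSS] = 1000 − 24 − 26.5 = 949.5. Reported variance is (949.5/78)/160 = 0.0761; true variance is 265/1600 = 0.1656. SE ratio 0.678, so type I error is about 2Φ(−1.96 × 0.678) = 18.4%.

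**Weekly means.** A constant patient level moves all five means together and drops out, so the test holds its level under CS. Variation in patient slopes is absorbed by the fitted line and never reaches the residuals. In the third example the ratio of reported to true variance is 4/(4 + 10 × 2.25) = 0.151, so the SE ratio is 0.389. On 3 df, P(|t| > 3.182 × 0.389) is about 30%.

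**Simulated type I error at nominal 5%, no true slope.** The first two rows use 60,000 trials with 17 and 16 patients; the others use 20,000 trials with 16 per arm. Random-slope rows give intercept variance, slope SD and residual variance.

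| Assumed structure | Scores, within arm | Scores, between arms | Means, within arm | Patient slopes, between arms |
|---|---|---|---|---|
| CS 0.3 / 0.5 / 0.7 | 2.1 / 0.8 / 0.1% | 2.1 / 0.7 / 0.1% | 5.0 / 5.0 / 5.1% | 4.9 to 5.1% |
| AR(1) 0.3 / 0.5 / 0.7 | 7.4 / 7.8 / 5.6% | 7.4 / 7.8 / 5.6% | 9.1 / 12.8 / 17.9% | 4.9 to 5.1% |
| AR(1) 0.8 / 0.9 | 3.4 / 0.8% | 3.0 / 0.6% | 21.0 / 24.3% | 4.8 / 5.1% |
| Random slopes 8, 0.5, 8 | 1.8% | 1.7% | 7.0% | 5.2% |
| Random slopes 8, 1, 8 | 5.5% | 5.4% | 12.3% | 4.9% |
| Random slopes 8, 1.5, 6 | 12.0% | 11.5% | 23.5% | 4.9% |
| Random slopes 4, 1.5, 4 | 18.4% | 18.4% | 30.2% | 5.0% |

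A line through weekly means compared between arms gave about 5% under CS and 10.6 / 16.0 / 22.8% under AR(1) 0.3 / 0.5 / 0.7. A separate run of 40,000 trials per setting with 17 and 16 patients agreed with the table to within 0.7 percentage points.

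The upper end for individual scores depends on where patients' lines spread. With the random intercept placed at the first score instead of mid-course, the individual-score error was 3.4% to 9.2%.

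Patient slopes compared between arms with 10% or 20% of scores missing at random gave 4.6% to 5.2%. The mixed model was not simulated.

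**The case against.** The strongest reply is that the defect is read from silence. The section says only that linear regressions were done, and a per-patient slope method is not excluded. It also attaches no p-value, CI or hypothesis to the slopes. This stands: the point is that the model is unspecified, and the miscalibration follows only if the text is read as ordinary regression and inference is drawn from it. It does not dispose of the point, because the 0.05 rule covers the regressions and the neighbouring analyses do state how they treat repeated scores.

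A second reply is that little depends on the regressions and that the larger error rates need particular assumptions (weekly means, or strongly varying slopes). This also stands, and it sets the priority.

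Two stronger readings are tempting and are not supported.
- A reader might infer that the trial's efficacy test is compromised. It is not: efficacy rests on the interaction in a repeated-measures ANOVA.
- A reader might infer that the per-group paired t-tests are meant to show tDCS against sham through a significant result in one arm only. The plan states no such inference, the paired tests are valid for change within an arm, and the same sentence supplies the unpaired between-arm test.

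**Conclusion.** The point holds as a minor one. As written, the regressions do not identify a model that respects repeated scores, and under the plain reading slope inference can err either way. For individual scores, type I error is about 0.1% to 8% under constant or AR(1) correlation, and up to about 18% with varying patient slopes. For weekly means it is about 5% under constant correlation and roughly 7% to 30% within an arm under AR(1) or varying slopes. All these figures rest on assumed correlations and an assumed 17/16 split, so they illustrate the problem and do not bound it. It would be wrong to infer that the regressions necessarily overstate the trend: under constant correlation, individual-score regression understates it.

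The primary interaction, the sample size, the paired t-tests and the planned unpaired change test are unaffected.

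**What to change.** State the model. Estimate one least-squares slope per patient from the available scores and compare these slopes between arms with an unpaired t-test. Alternatively, fit a mixed model with random intercept and slope and a group × time term. Report the between-arm slope difference with its 95% CI as supportive, and show the per-group lines as descriptive only. State that efficacy continues to rest on the interaction already named as primary. If this is not done, label the regressions descriptive and report no p-values from them.

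The cost is a few sentences and a small re-analysis of existing data. Participants "were recruited between June of 2015 and April of 2018" and the document is dated October 2018, so the change must be reported as specified after data collection. It adds one more between-arm comparison on the same scores, beside the change test and any between-arm Bonferroni-corrected t-tests, and it assumes a linear course. For both reasons it should stay supportive. Sample size and data collection do not change.

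### The supporting between-arm t-test on craving change fixes the baseline slope at 1; an ANCOVA on the baseline OCCS already collected would be more precise over most plausible inputs

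*Combined protocol and SAP*

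**What the plan says.** The Statistical Analysis section makes the "craving measurements x condition interaction as the primary outcome parameter" in a two-way mixed ANOVA over five time-points. It then lists supporting analyses. One is within-arm: "Additional comparisons between initial and final OCDS scores were done by paired t-tests for each group". The other is between arms: "differences between final and initial scores were compared between sham-tDCS and real tDCS groups with unpaired t-test". Effect sizes for the unpaired tests are to be given as Hedges's g_s.

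That sentence names the OCDS. The scale described under Craving assessment is the five-item OCCS, scored 0 to 20, and I take the two to be the same instrument. Craving assessment also shows that a baseline exists: "The OCCS was applied in the week before the beginning of the real or sham-tDCS treatment". Under Procedures, patients were "randomly assigned to one of the two groups (sham- and real tDCS) in a 1:1 ratio". No analysis in the document uses baseline craving as a covariate. In the primary ANOVA the baseline score enters as one of the five levels of the time factor.

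**The concern.** A change score does use the baseline, but only by subtraction. This amounts to assuming that each extra point at baseline predicts exactly one extra point at the end. When the true slope is below 1, as it usually is when scores regress towards the mean, subtraction over-corrects and adds noise. An ANCOVA estimates the slope and removes that noise.

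The stake is the width of the confidence interval and the power of the one analysis that summarises start-to-end benefit as a single signed difference between arms. Validity is not at stake: both estimators are unbiased under randomisation, and the shift that a chance baseline gap causes in one trial is how the precision is lost, not a separate bias.

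**Working it through.** **The plan's own figure.** The plan states a minimum of 30 participants.
- Partial eta squared 0.10384 gives f² = 0.10384/0.89616 = 0.1159, so f = 0.340.
- With the SPSS-type G*Power convention, five time-points and sphericity assumed, λ = f²(N−2)(5−1), on 4 and 4(N−2) df.
- The minimum is 29, or 30 with equal arms (power 81.8% at 30). Then 30 × 1.10 = 33, as stated.

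That calculation concerns the primary interaction and is not affected by what follows.

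**Inputs.**
- Analysed N: 35 recruited minus 2 excluded (Participants) = 33, which is also the planned total.
- ρ, the correlation of baseline with final OCCS, and k = final SD / baseline SD: neither is in the documents, so both are varied.

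**Variance formulas** (baseline SD set to 1; the common factor 1/n₁ + 1/n₂ cancels in the ratio, so the arm split does not matter):
- Change score: k² + 1 − 2ρk.
- ANCOVA: k²(1 − ρ²) × [1 + 1/(N−4)]. The bracket is the expected cost of estimating the slope; at N = 33 it is 30/29.
- Ratio, ANCOVA to change score: [1 − (1 − ρk)²/(k² + 1 − 2ρk)] × 30/29.

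The subtracted term cannot be negative, so the ratio never exceeds 30/29 = 1.034. It reaches that ceiling when the true slope ρk equals 1.

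**Break-even at k = 1.** The ratio reduces to (1 + ρ)/2 × 30/29, which equals 1 at ρ = 2 × 29/30 − 1 = 0.933 (0.926 at N = 30, 0.938 at N = 35).

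**Variance ratios at N = 33:**

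| k | ρ 0.3 | ρ 0.5 | ρ 0.7 | ρ 0.8 | ρ 0.9 |
|---|---|---|---|---|---|
| 0.8 | 0.52 | 0.59 | 0.65 | 0.66 | 0.63 |
| 1 | 0.67 | 0.78 | 0.88 | 0.93 | 0.98 |
| 1.25 | 0.81 | 0.92 | 1.01 | 1.03 | 0.98 |

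For example, at k = 0.8 and ρ = 0.5: 0.64 × 0.75 = 0.48; 0.64 + 1 − 0.80 = 0.84; 0.48/0.84 × 30/29 = 0.59.

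**Where the change score is the more precise:** ρ of about 0.80 to 0.96 at k = 1.1, 0.66 to 0.89 at k = 1.25, and 0.51 to 0.78 at k = 1.5. At k = 0.9 or below there is no such range.

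**Power illustration.** This assumes a true difference of 0.8 baseline SD, which is not in the documents, and arms of 16 and 17. It uses the noncentral t (31 df for the change score; 30 df for ANCOVA, averaged over the baseline distribution). For the change score at k = 1 and ρ = 0.5, the noncentrality is 0.8/√(1 × 0.1213) = 2.30. Power, change score then ANCOVA:

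| k | ρ 0.5 | ρ 0.7 | ρ 0.8 |
|---|---|---|---|
| 0.8 | 68%, 88% | 87%, 97% | 96%, 99.5% |
| 1 | 60%, 71% | 82%, 86% | 94%, 95% |
| 1.25 | 49%, 52% | 69%, 69% | 84%, 83% |

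Simulation with 40,000 trials in each of 15 settings agreed: variance ratios within 0.006, power within 1 point, and type I error between 4.7% and 5.2% for both tests.

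**Timing.** Recruitment ran to April 2018. Procedures says that before stimulation "they were maintained under regular treatment for 30 days in average", then gives five weeks of stimulation and 60 days of follow-up. From 30 April 2018, 30 + 35 + 60 days ends on 2 September 2018, 51 days before the document date of 23 October 2018. Participants and experimenters were "blinded for brain stimulation assignments from the beginning of the study protocol up to the end of the 60-days follow-up". The Statistical Analysis section also already describes the data: "Most of data (age, patterns of crack-cocaine use, 5-items OCCS) were normally distributed". It is therefore likely, though not stated, that blinding had ended.

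**The case against.** The strongest reply is that nothing here is an error. The test is valid, it is one of several supporting comparisons, and the first-to-last change compared between arms is a natural contrast of the primary interaction. All of that stands, and it is why the primary analysis should be left alone and the planned t-test kept if the data have been seen.

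A second reply is that the gain rests on unseen inputs. The 0.93 holds only for equal SDs. At k = 1 and ρ of 0.7, 0.8 and 0.9, the confidence interval is only about 6%, 3% and 1% narrower, and at k = 1.25 with ρ of 0.7 or 0.8 it is 1% to 2% wider. The most striking power contrast needs both k = 0.8 and ρ = 0.5. This is fair as to size. It does not overturn the advice, because the downside is capped whatever ρ and k are, while the possible saving is not small.

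A third reply is that a post hoc ANCOVA adds another test to a list with no stated multiplicity control for the additional comparisons. That stands: on that route it is a sensitivity analysis and cannot restore pre-specified power.

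Two details also stand. Counting the larger critical value (30 instead of 31 df), the worst case is 3.7% in squared interval width and the break-even is 0.928. And the date is approximate: the 30 days is an average, follow-up is tied in places to discharge and in places to the end of stimulation, and ten sessions on alternate days span about 19 days, not 35. None of this changes the recommendation.

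**Conclusion.** The point holds as a low-priority improvement. The planned between-arm comparison of change is valid but gives up precision over most plausible values of ρ and k. With equal SDs, adjustment saves about 22% of variance at ρ = 0.5, 12% at 0.7 and 7% at 0.8. If the final SD is 0.8 of the baseline SD, it saves at least 34% at any positive ρ. If the final SD is larger than the baseline SD, the gain can vanish or reverse, by at most 3.4% of variance. These figures rest on 33 analysed patients, a linear relation of final to baseline score and a roughly normal baseline. ρ and k are assumptions that the trial's own data can settle.

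**What to change.** For this comparison, report an ANCOVA of the fifth OCCS score on group and baseline OCCS, giving the adjusted difference in scale points with its 95% CI.
- **If the data are still blinded:** specify the ANCOVA in place of the change-score t-test, and say whether Hedges's g_s will still be reported for the change.
- **If blinding has ended, as the timings suggest:** keep the planned t-test and its effect size, add the ANCOVA labelled post hoc, and report it whatever it shows.

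Leave the primary interaction and the sample size of 30 unchanged, and add no other covariate.

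The cost is one extra model on data already collected. Estimating the slope uses one degree of freedom and costs about 3.4% of variance at N = 33 (27/26, or 3.8%, at N = 30) before any saving.
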